| Study Design | Co-Primary Objective, Acute Pain: To determine whether multimodal M-Stim reduces Pain Intensity 30% more than TENS in the first 10 days after presenting for treatment. Co-Primary Objective, Chronic Pain: To determine whether multimodal M-Stim reduces disability 30% more than TENS at 6 months. A randomized, double-blind controlled trial with 3- (aLBP) or 6- month (cLBP) follow-up. |
|-------------------------|--|
| Study Setting | The study will be conducted at mixed physical therapy/chiropractic practices in Washington, DC, Maryland, and Virginia, which offer demographic and economic diversity. These clinics provide an ideal environment, with frequent follow-ups and ongoing therapy but no onsite access to opioid prescribers. |
| Eligibility Criteria | Inclusion Criteria: - Male or female adults aged 18-90 presenting for treatment of acute or chronic low back pain - Self report of moderate to severe LBP of 4 or greater out of 10 on a 0-10 Numeric Rating Scale. - Acute: pain duration <3 months not using opioids for the current exacerbation of low back pain - Chronic: Pain duration >= 3 months with or without ongoing opioid use - Capacity to understand risks and benefits (informed consent). - Smartphone for Qualtrics web-based platform use Exclusion Criteria: - Radicular pain likely reflecting a surgical or mechanical problem - Inability to apply or use the device - Sensitivity to cold or vibration (e.g Raynaud's or Sickle Cell Disease) - Diabetic neuropathy rendering a patient unable to determine if the device is too hot - New neurologic deficits, skin lesions over the low back area - A contraindication to any medication for pain management that would impact analgesic use record |

| | - Pacemaker |
|--------------|---|
| Intervention | The experimental arm DuoTherm is a novel multimodal low back pain relief device incorporating 8 harmonic vibration patterns of mechanical stimulation (M-Stim) including neuromodulatory frequencies, 5 intensity levels, and optional heat, cold, and pressure delivered through a sculpted metal plate attached with a belt and controlled by buttons on the belt. Patients will be instructed to use the device at least daily for 30 minutes. The active control is a prescription 4-lead 8-channel TENS unit (LG Smart) with variable intensity. |

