| | Participants will be instructed to use the device for a minimum of 30 minutes a day. Both M-Stim and LG Smart TENS groups will receive a standard pain management regimen typically used for low back pain standardized across all clinicians participating in the study. Participants will keep the devices and be instructed to use them for pain as needed during the duration of the study. |
| Outcomes | Opioid Use Primary Outcome: |
| | Prior use: For patients with prior or ongoing opioid use, a 30% reduction in MME (Milligram Morphine Equivalents) between the first 14 days and the last 14 days of daily diary recordings using the DOSE data collection tool. |
| | Opioid naïve: 30% reduction of those receiving an opioid prescription "prescribed to me for this event" |
| | Secondary outcomes: Use days; total MME and use past 7 days in the opioid naïve; use days by those with more severe pain using the NIH Research Taskforce definitions; and prescribing compared to a contemporaneous national LBP population (25%). |
| | Pain Primary Outcome: |
| | Chronic: 30% lower disability at 6 months using PROMIS Pain Interference for those with ongoing pain >3 months |
| | Acute: 30% lower NRS 0-10 "pain now" from entry to 10 days for those presenting with an episode of pain starting within the past 2 weeks |
| | Secondary Outcomes: Change in disability for those with >=57.7 PROMIS Pain Interference; restoration of function to normal (PI=50); |

| | integrated analysis with | n common | criteria fo | r restoration | on of function | on with | |
|-------------------------|---|---------------|--------------------|---------------------|----------------------|----------------------------|--|
| | multifidus stimulation s | surgery. | | | | | |
| | | | | | | | |
| Participant Timeline | | Initial Visit | Daily x 28 days | Weekly for 3 months | Monthly for 3 months | Monthly 4 - 6 months | |
| | Consent, Enrollment, Randomization | ALBP, CLBP | | | | | |
| | Minimum Dataset, Pain Catastrophizing Sullivan, PROMIS Depression, Physical Function | ALBP, CLBP | | | | | |
| | NRS (at that moment & past 24 hours) | ALBP, CLBP | ALBP, CLBP | ALBP, CLBP | ALBP, CLBP | CLBP | |
| | NRS after 30 minutes | ALBP, CLBP | | | | | |
| | NRS Past week | | | ALBP, CLBP | ALBP, CLBP | CLBP | |
| | NRS Past month | | | | ALBP, CLBP | CLBP | |
| | PROMIS Pain Intensity, Pain Interference | ALBP, CLBP | | ALBP, CLBP | ALBP, CLBP | CLBP | |

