| Blinding (masking) | Participants were blinded to which device powered the study hypothesis, and blinded to their assigned intervention until after documenting initial NRS pain intensity. Success of blinding the study device (M-Stim) versus the active control (TENS) was tested at months 3-6 with prompts, "select which group you think you were in (control or treatment)" and "How confident are you (0 = Least Confident 100 = Most Confident)." The protocol statistician and study coordinator knew the intervention assignments during enrollment but did not conduct statistical analysis. The PI and treating chiropractor were blinded to allocation during enrollment, with the PI accessing data only after study completion. The analyzing statistician was blinded to device assignment until completion of data cleaning and initial analysis. |
| Data Collection Methods | Site coordinators entered identification and contact information after informed consent on a tablet, then recorded weight, height, and duration to confirm acute or chronic follow-up duration, then participants took the tablet to record pain intensity on a 0-10 NRS now and past 24 hours. While using the device for 30 minutes, participants completed 7-day pain intensity NRS, NIH Back Pain Research Minimum Dataset, including PROMIS measures of Physical Function, Pain Interference, Depression, and Catastrophizing via the Sullivan Catastrophizing scale, Injury Mechanism, prior treatments, exercise and athletic status. |
| | Participants were prompted to record analgesic use, pain, and device use daily for a month on the web-based platform, then weekly, with the monthly surveys adding Pain Interference. All surveys asked about |

analgesic use. Due to the anticipated heterogeneity of opioid formulations, a skip-logic data collection instrument algorithm was created with robust options for Dose per pill (34), Opioid formulations, e.g. hydrocodone, hydromorphone etc. (15) and the Source (DOSE tool, Supplement 2). Sources included "prescribed to me for this event", "prescribed to me for another event", "given to me by a family member", "given to me by a friend", "given to me by an acquaintance or stranger", or "purchased from someone without a prescription". These were converted to a total milligram morphine equivalent (MME) for analysis.

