Participants recorded when they used their device, duration of use, and any additional pain relief modalities (exercise, stretching, bath, hot tub, therapy, massage). Patients were asked to record any thermal use or therapy cycle or channel as appropriate to their device.

Participants verbally endorsing pain for less than three months (acute) were entered into a 3 month follow-up program, or 6 months (chronic) for those for whom back pain had been an ongoing problem for more than 3 months.

Statistical Methods

Statistical analysis was performed with masked intervention allocation by a statistician new to the project to determine differences in primary and secondary outcomes.

An intention-to-treat analysis included all participants meeting inclusion criteria. Summary statistics (means, standard deviations, proportions) were calculated using T-tests and Chi-squared tests. Opioid prescribing differences were calculated with raw percent of change and relative risks. Diary entries and item-level data were analyzed for missing data to assess the need for imputation. Relative risks were calculated for MME and opioid use days between intervention groups, with paired T-tests used to compare first two and last two weeks of MME in those who used opioids during the study. A linear regression assessed BMI's interaction with opioid use, calculating marginal effects with standard errors via the Delta Method. Data analysis was performed using STATANow/SE 18.5.

For pain outcomes, in addition to the above methods, missing 10 day NRS-1 data will be imputed using forward fill and KNN. A neural network will be created to determine factors contributing to 13 week Pain Interference, with iterative modeling to reduce mean absolute error. Graphs with r-squared for predictors will be generated.

| Data Monitoring | Data collection was conducted through an app that tracked daily pain, opioid use and device usage. Monitoring included weekly enrollment review by the protocol statistician to assess comprehension of the data collection tool. Adverse events were reported as per protocol. | |
|------------------------|---|--|

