monthly surveys added past month NRS, Blinding assessment for additional 3 months for those started in chronic strata. Added "source" for each opioid use case to DOSE tool collecting opioid formulation, dose, and number of pills. We intended to use evaluate change in MME over time for chronic opioid users. The FDA recommended requiring participants on opioids maintain dosage and frequency. As we did not have access to prescribing records, and opioid reduction was a desired outcome measure, we evaluated opioid use for the first two weeks versus the last two of those endorsing prior opioid use. We extended the baseline and follow-up Pain Intensity measurements to one month rather than one week. 3a) 8/31/22 – Site Visit. PI noted staff using "will not fit" criteria rather than BMI of 30 from pilot study. New device fits variable BMI, based on abdominal girth. Retained "if device fits", exclusion criteria using BMI changed to BMI >50, noting controversy in using BMI as exclusion criteria. 4) 5/5/23; Added "Do you think you will need surgery" and "do you think you will need epidural" questions, and "did you get surgery" and "did you get an epidural" to monthly. 5) 7/13/2023 New Location added Stratification by chronicity versus opioid use status: enrollment strata were based on verbal endorsement of duration and no acute opioid use for back pain. Initial evaluation of registration data after enrollment was complete revealed 16 of 60 in the "acute" strata reported a duration longer than three months, and half in each chronicity strata no prior opioids for LBP. In consultation with Clinical Trials.gov, we pooled the data and included both opioid and pain outcomes as a single NCT04491175 registry with two different publications and analyses. Informed Informed consent will be obtained from each participant after screening. Consent Participants will be informed about the voluntary nature of the study, with a HIPAA form for confidentiality. Consent will be documented via selecting 'continue' on the digital consent form. Confidentiality Patient data will be stored on password-protected network drives. All data will be de-identified using a unique study ID for each participant. Confidential records will be stored in secure, restricted-access rooms. Declaration of The principal investigator has financial conflict of interest from design interests and research into the DuoTherm device, and creating a company to

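### No rule is stated for the prescribing status of opioid-naive participants who stop responding; by default they count as not prescribed, so the crude prescribing result can move with survey return

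*Combined protocol and SAP*

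**What the plan says.** All references are to the combined protocol and SAP.

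- **Endpoint.** Outcomes sets the opioid-naive primary as a "30% reduction of those receiving an opioid prescription" for the present episode. A secondary outcome compares prescribing with a contemporaneous national rate of 25%.
- **Where the event comes from.** Data Collection Methods says: "Participants were prompted to record analgesic use, pain, and device use daily for a month on the web-based platform, then weekly", with monthly surveys as well. The category that defines the endpoint is one answer to the source item of the DOSE tool. Under Protocol Amendments that item was added "for each opioid use case to DOSE tool collecting opioid formulation, dose, and number of pills", so it is filled only when a participant reports taking an opioid.
- **No second source.** Protocol Amendments says: "As we did not have access to prescribing records". Study Setting describes clinics with "no onsite access to opioid prescribers".
- **Analysis.** Statistical Methods says: "An intention-to-treat analysis included all participants meeting inclusion criteria". For this endpoint: "Opioid prescribing differences were calculated with raw percent of change and relative risks".
- **Missing data.** The same section says diary and item-level data were examined to see whether imputation was needed. The only imputation it specifies is for the day-10 pain score.
- **Follow-up.** Study Design gives 3 months for acute and 6 months for chronic participants. Protocol Amendments reports that about half of each stratum had no earlier opioids for back pain, and that the strata were then pooled.

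**The concern.** A prescription enters the data only through a returned survey that reports opioid use. A participant who was never prescribed an opioid and one who fell silent before being prescribed one leave the same record, which is an empty source item. A raw percentage over an intention-to-treat set, with no rule that separates the two, treats both as not prescribed.

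Two results are exposed. The between-arm relative risk moves if survey return differs by device. That is plausible: the devices differ, participants know which one they hold once the initial pain score is recorded, and the data depend on self-completed surveys over months. The comparison with 25% is exposed even when loss is equal, because missed prescriptions lower the trial's rate.

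Pooling adds a smaller problem. A percentage that mixes 3-month and 6-month follow-up has no single time horizon. Randomisation within strata should keep the mix similar between arms, so this blurs what the rate means more than it biases the ratio.

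**Working it through.** **The plan's own figures.** The plan gives no response rate for this endpoint. Its 17 per group for prescribing reproduces as a t-test with effect size 1, two-sided 0.05 and 80% power (power assumed). That calculation includes nothing for loss and does not bear on this point. Sample Size cites 20% from a previous study without saying of what.

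**Inputs from the documents.** Reference rate 25% and target reduction 30% (Outcomes; read as relative here, because the plan does not say). Planned size 60 + 100 = 160 (Sample Size), about half opioid-naive (Protocol Amendments): 80, or 40 per arm if allocation is 1:1.

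**Assumptions.** True prescribing p = 25% in both arms. r is the share of an arm that responds throughout. h is the share of lost participants' prescriptions that were reported before loss. Prescribing is unrelated to loss unless stated.

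**Step 1: formula.** If silence is scored as no event:

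observed rate = p × [r + (1 − r) × h]

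With h = 0, observed RR = true RR × (M-Stim response ÷ TENS response). With h = 1 there is no distortion. The response ratio is therefore the limit of the effect under these assumptions.

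**Step 2: unequal response, true RR 1.00.**

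| M-Stim / TENS response | h | Observed rates | RR |
|---|---|---|---|
| 80% / 90% | 0 | 20.0% / 22.5% | 0.89 |
| 70% / 90% | 0 | 17.5% / 22.5% | 0.78 |
| 70% / 90% | 0.5 | 21.25% / 23.75% | 0.89 |
| 63% / 90% | 0 | 15.75% / 22.5% | 0.70 |
| 90% / 70% | 0 | 22.5% / 17.5% | 1.29 |

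For h = 0.5: 0.25 × (0.70 + 0.15) = 0.2125; 0.25 × (0.90 + 0.05) = 0.2375; ratio 0.89. The 63% / 90% row produces the whole 30% target with no device effect.

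With 40 per arm, h = 0 and a two-sided chi-square test at 5%, rejection under no effect rises from 5.0% to 8.7% at 70% / 90%.

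**Step 3: equal response of 80%, h = 0.** With 25% in both arms, each reads 0.25 × 0.80 = 20% and RR stays 1.00. With a true 25% versus 17.5%, the arms read 20% versus 14%. RR stays 0.70, but the difference shrinks from 7.5 to 6 points. Against the external 25%, a trial rate that is truly 25% looks 5 points lower.

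**Step 4: dependence on the unstated rule.** Take 40 per arm, 7 versus 10 reported prescriptions and 8 versus 4 non-responders (illustrative counts, M-Stim first).
- Scored as not prescribed: 7/10 = 0.70.
- Responders only: (7/32) ÷ (10/36) = 0.79.
- All non-responders prescribed: 15/14 = 1.07.
- Extremes: 7/14 = 0.50 to 15/10 = 1.50.

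**Step 5: what censoring can and cannot do.** If loss is unrelated to prescribing, restricting to observed time recovers RR 1.00 in every row of Step 2. Suppose instead prescribing is 20% in those retained and 40% in those lost, with 30% versus 10% lost at the start. The true rates are 0.20 × 0.70 + 0.40 × 0.30 = 26% and 0.20 × 0.90 + 0.40 × 0.10 = 22%, RR 1.18. Scoring silence as no event gives 0.14/0.18 = 0.78, and censoring gives 1.00. Censoring is closer to the truth but not right.

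**Step 6: why sensitivity analyses must be symmetric.** In the 70% / 90%, h = 0 case, counting only lost M-Stim participants as prescribed gives (17.5% + 30%) ÷ 22.5% = 2.11 when the truth is 1.00. The same assumption in both arms gives 47.5% ÷ 32.5% = 1.46. That is still an extreme, so a graded analysis is needed.

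**The case against.** The strongest reply is that the plan nowhere says a non-responder is scored as not prescribed. A reader might infer such a rule, but the documents leave it open. The default reading follows from combining intention to treat, a raw percentage and an item filled only on a positive report. That correction stands.

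Three other stronger readings also fail.
- A reader might take the intention-to-treat sentence to put every participant in this denominator. It is trial-wide, and Outcomes defines this endpoint for the opioid-naive.
- A reader might conclude that missing data were ignored. The DOSE items sit in the surveys whose missingness was reviewed, so the review reaches them. What it lacks is a trigger, a method or a rule for prescribing status.
- A reader might infer that the bias favours M-Stim. Participants with poor relief may stop answering, but so may those who recover. The documents support neither direction.

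It is also fair to say that the DOSE items are collected at baseline and daily for 28 days, so early prescriptions may be reported before loss. That is why 0.78 is the limit for that response pattern and 0.89 is shown beside it. No document supports any particular split in response.

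Finally, Kaplan-Meier assumes uninformative censoring, and Statistical Methods describes part of the analysis as done. Both objections stand and shape the remedy. Neither supplies the missing rule.

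**Conclusion.** The point holds as a gap in the specification of a primary outcome. The prescribing status of opioid-naive participants who stop responding is undefined, and the natural default counts them as not prescribed over pooled 3- and 6-month follow-up.

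The size is conditional. With response of 70% versus 90% and a true 25% in both arms, the relative risk reads 0.78 at the limit and about 0.89 if half of the lost participants' prescriptions were reported first. Reversing the response rates at the limit gives 1.29. These response rates are assumptions, and the direction is unknown. Equal loss does not bias the relative risk under these assumptions, but 20% loss before any prescription turns 25% into 20% in the external comparison. The documents do not show that any such bias occurred.

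**What to change.** **Primary estimate.** In the opioid-naive set, estimate the risk of a first report of an opioid prescribed for this episode by Kaplan-Meier, from randomisation, censored at the last returned survey. Report it by arm at a common day 90, with risk difference, risk ratio and 95% confidence intervals, stratified by the acute or chronic stratum used at randomisation. Use the same estimate for the comparison with 25%.

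**Survey return.** Tabulate returned surveys by arm and time.

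**Sensitivity.** Because censoring may be informative, add a tipping-point analysis that varies the assumed prescribing rate among those lost in both arms. Include the case in which the same worst-case assumption is applied to each arm, and state the combination at which the conclusion changes.

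**Status.** State how non-responders were classified in any analysis already run, and label the new one a post hoc re-analysis.

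**Cost.** SAP wording and analysis time, with no new data collection provided the web platform holds survey dates. Intervals become slightly wider, and months 4 to 6 of the chronic stratum have to be reported separately.

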| | Dose, Opioid formulation, number Source (DOSE tool), other analgesics | ALBP, CLBP | ALBP, CLBP | ALBP, CLBP | ALBP, CLBP | CLBP | |
| | Device usage | | ALBP, CLBP | ALBP, CLBP | ALBP, CLBP | CLBP | |
| Sample Size | To estimate the M-Stim | interventi | on effect : | size, a retro | spective st | udy of | |
| | 59 cLBP patients on ch | ronic opioi | ds (100% | prolonged | opioid use) | | |
| | reported a 28% reducti | on in MME | after spin | al stimulat | or | | |
| | implantation,[40] reducing MME 26.2(SD32.8) compared to 5.8(SD34.2) | | | | | | |
| | for those with conventional treatment (effect size 0.60. A priori, we would | | | | | | |
| | be able to detect an effect size of 1 (meaning a difference of 1 standard | | | | | | |
| | deviation) with 94% power and alpha of .03 using a Wilcoxon Mann | | | | | | |
| | Whitney test with 30 in each group. With this effect size for a two-sided | | | | | | |
| | significance of 0.05, 17 participants per group would detect a 30% | | | | | | |
| | prescribing reduction, while 50 participants on chronic opioids per | | | | | | |
| | treatment group would provide 85.4% power to detect a 30% reduction in | | | | | | |
| | MME. Given the 20% in a previous study by Jamieson et al, we increased | | | | | | |
| | the cLBP sample to 50 | - | | Jannoson | icat, we iiio | ioasea | |
| | | | | | | | |

| | We planned to recruit 60 aLBP participants who had never taken opioids for their back pain, and 100 cLBP without a new prescription but with or without chronic opioid for cLBP. |
|----------------------------|--|
| Recruitment | Patients were recruited from Kaizo Health Centers in Landover and Fairfax, through direct referrals, flyers, and digital content like social posts and emails targeting local populations. Flyers were also distributed at three local pain clinics. |
| Randomization | After eligibility screening and informed consent, a 4-digit participant ID and the intervention allocation were randomly assigned by the survey software to either the DuoTherm or LG Smart TENS group within acute and chronic arms. A copy of the informed consent was emailed to the participant. |

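### A relative risk is the between-arm measure named for MME and opioid use days, but no event is defined for MME and no unit of analysis or variance method is given for use days

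*Combined protocol and SAP*

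**What the plan says.** In the Statistical Methods section, the between-arm statement for amount of opioid is: "Relative risks were calculated for MME and opioid use days between intervention groups". The sentence continues "with paired T-tests used to compare first two and last two weeks of MME in those who used opioids during the study". Prescribing has its own sentence: "Opioid prescribing differences were calculated with raw percent of change and relative risks". A more general sentence links summary statistics with t-tests and chi-squared tests, without naming MME or use days.

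Under Data Collection Methods, the DOSE entries become an amount: "These were converted to a total milligram morphine equivalent (MME) for analysis". Under Outcomes, the primary opioid outcome for people with prior or ongoing use is "a 30% reduction in MME (Milligram Morphine Equivalents) between the first 14 days and the last 14 days of daily diary recordings". The secondary opioid outcomes begin "Use days; total MME and use past 7 days in the opioid naïve". The primary opioid objective is worded as a comparison with TENS. The Participant Timeline gives 28 daily entries per person.

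The Sample Size section gives 85.4% power for MME with 50 people per group, based on mean MME reductions with their SDs.

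**The concern.** A relative risk is a ratio of two probabilities. It needs a defined event and one yes/no result per independent unit. The prescribing outcome has these. MME does not: no cut-off or response definition is attached to the sentence that names the relative risk. For use days, the plan leaves open whether the unit is the person or the diary day, and how the variance is computed.

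This matters because MME carries a primary outcome, and total MME and use days are listed as secondary outcomes. Two competent analysts could follow the sentence and produce different estimates with very different intervals. Some of the possible readings cannot see a change in dose, and one would give intervals that are far too narrow.

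**Working it through.** **1. The plan's own power figure.** Inputs from the Sample Size section: reductions of 26.2 (SD 32.8) and 5.8 (SD 34.2), 50 per group, two-sided 0.05.

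- Pooled SD = √[(32.8² + 34.2²)/2] = 33.5
- d = (26.2 − 5.8)/33.5 = 0.609
- Two-sample t-test (noncentral t), n = 50 per group: power 85.4%

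The stated figure reproduces. The powered comparison is therefore between arms, at person level, on mean MME reduction.

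**2. The analyses named, set against that comparison.**

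| Named analysis | Compares arms? | Applies to amount of MME? |
|---|---|---|
| Relative risk for MME and use days | Yes | Not defined without an event |
| Paired t-test, first versus last two weeks | No, periods within persons | Yes, in opioid users only |
| Percent change and relative risk for prescribing | Yes | No, yes/no outcome |
| General t-test and chi-squared sentence | Not stated | MME not named |

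No row names the comparison that was powered.

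**3. What the relative risk could mean.**

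- *Any MME, yes or no.* Valid, but if a share p of each arm uses any opioid, the relative risk is p/p = 1 however far the dose falls among users in one arm. It has no power for a dose reduction.
- *A 30% MME reduction achieved, yes or no.* Valid and sensitive to dose, with one result per person. The Statistical Methods section does not say this is meant.
- *Ratio of mean MME or mean use days per person.* Sensible, but not a relative risk, and no variance method is given.
- *Pooled diary days.* Each day counts as a separate unit. The plan neither states nor excludes this.

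**4. Size under the pooled-day reading only.** With m days per person and within-person correlation ICC:

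- Design effect = 1 + (m − 1) × ICC
- True SE / naive SE = √(design effect)
- True type I error of a nominal 5% test = 2 × [1 − Φ(1.96/√(design effect))]

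Example: m = 28, ICC = 0.3 gives 1 + 27 × 0.3 = 9.1, √9.1 = 3.02 and a type I error of 51.6%.

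| Assumed ICC | SE factor, 28 days | Type I, 28 days | SE factor, 14 days | Type I, 14 days |
|---|---|---|---|---|
| 0.05 | 1.53 | 20.1% | 1.28 | 12.7% |
| 0.1 | 1.92 | 30.8% | 1.52 | 19.6% |
| 0.2 | 2.53 | 43.8% | 1.90 | 30.2% |
| 0.3 | 3.02 | 51.6% | 2.21 | 37.6% |
| 0.5 | 3.81 | 60.7% | 2.74 | 47.4% |
| 0.7 | 4.46 | 66.0% | 3.18 | 53.7% |
| 0.9 | 5.03 | 69.7% | 3.56 | 58.2% |

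The ICC at which the SE is k-fold too small is (k² − 1)/(m − 1). Two-fold needs 3/27 = 0.11 over 28 days or 3/13 = 0.23 over 14. Three-fold needs 8/27 = 0.30 or 8/13 = 0.62.

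**5. Simulation check.** Null trials were simulated with 30 to 80 people per arm, 28 days, and assumed shares of users and use probabilities, giving ICCs of about 0.05 to 0.62. The pooled-day relative risk had a median SE ratio of 1.5 to 4.2 and rejected in 19% to 66% of trials. A person-level ratio using between-person variance rejected in 4.4% to 7.4%.

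**The case against.** The strongest reply is that the plan is terse rather than wrong. It nowhere says that diary days are pooled or treated as independent. A reader might infer that it does, and that its standard errors are therefore several-fold too small. The documents do not support that inference: they are silent on the unit and the variance method, and they give no ICC. This part of the objection stands in full, so the inflation figures are conditional.

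Second, the general t-test sentence could cover a between-arm comparison of person means for MME. This is possible, but that sentence concerns summary statistics and does not name MME. The sentence that does name MME assigns it a relative risk. The general sentence does not settle the question.

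Third, the Outcomes section offers a natural yes/no result, a 30% MME reduction, for which a relative risk is sound. That also stands as a possible reading, but the plan does not adopt it for this analysis.

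Finally, a reader might infer from "94% power and alpha of .03 using a Wilcoxon Mann" that a rank test had been planned for MME and then dropped. That sentence names no outcome, and the separate 85.4% figure for MME reproduces with a t-test, so the inference is not established.

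**Conclusion.** The concern holds as an ill-suited and under-specified between-arm method. A relative risk is assigned to a continuous amount with no event defined, and to use days with no unit or variance method. The person-level comparison of mean MME reductions behind the 85.4% is not among the analyses named for MME. These conclusions need no assumption beyond the text.

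The numerical size is conditional. If diary days were pooled as independent over 28 days, standard errors would be about 1.5 to 5 times too small and the type I error about 20% to 70%, for assumed ICCs of 0.05 to 0.9. Describing this as three-fold or more requires an ICC of at least about 0.30 over 28 days. It cannot be said from the documents that this error was made.

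The stated MME power is not in error on this point, and the sample size does not change because of it. Relative risk remains appropriate for the prescribing outcome.

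**What to change.** Replace the sentence on MME and use days with a person-level analysis:

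- **Total MME and number of use days.** Take one value per person. Compare arms as a ratio of means from a log-link quasi-Poisson model with person-level robust standard errors. Use log(reported days) as offset, and adjust for randomisation stratum (acute or chronic, as randomised) and MME from the initial-visit DOSE entry. The offset goes with totals only; combining it with per-day means would divide by days twice.
- **Prior-use primary outcome.** Compare the change in MME from the first to the last 14 days between arms, one change per person, with a rank test as a distribution-free check. Keep the paired t-test as a description of change over time.
- **Relative risk.** Keep it only for yes/no results counted once per person, such as prescription received or 30% MME reduction achieved. For the latter, state how people with no MME in the first window are handled.

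The cost is SAP wording and re-analysis of data already collected. Intervals may be wider. Because this section is largely in the past tense, the amended text should say whether the change was made before or after results by arm were seen.
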